## 9.2 Additional Analyses of the Primary Efficacy Endpoint

The Exit DBPCFC is defined as indeterminate if the subject was not able to tolerate the placebo challenge up to and including a dose of 600 mg (1043 mg cumulative). Also, prior to Protocol Amendment 3, subjects could be enrolled if they had an indeterminate Screening DBPCFC. The Screening DBPCFC will be considered indeterminate if the subject is not able to tolerate a dose of 100 mg (443 mg cumulative) of the placebo challenge. Subjects with an indeterminate DBPCFC (either at screening or exit) will be excluded for a sensitivity analysis of the primary efficacy analysis in this ITT subset.

The primary efficacy analysis will also be repeated in the mITT and PP populations as sensitivity analyses. These sensitivity analyses effectively assess the results by treating truly missing data as missing-at-random rather than by imputing a response.

## 9.3 Secondary Efficacy Analyses

All secondary analyses of key secondary endpoints will be performed in the ITT population.

The key secondary efficacy endpoints are:

- Peanut MTD at the Exit DBPCFC
- Change from baseline in the Peanut MTD at the Exit DBPCFC.

These will be tested in a hierarchical order. If the primary efficacy analysis is significant at the 0.05 level, then the MTD at Exit DBPCFC will be tested with a Type I error rate of 0.05. If this test is significant, then change from baseline in MTD at the Exit DBPCFC will be tested with a Type I error rate of 0.05. This closed testing procedure maintains the overall Type I error rate at 0.05. If the first test is not significant, the p-value for the change from baseline will be displayed for informational purposes only.

Sensitivity analyses of the key secondary efficacy analyses will be performed by excluding subjects with an indeterminate DBPCFC, as defined in Section 9.2, prior to performing the analyses on the ITT population. Analysis of key secondary endpoints will also be repeated in the mITT and PP populations as sensitivity analyses.

DBPCFC results will be listed at both time points, where applicable, for all randomized subjects. Screening DBPCFC results will be listed for screen failures. Composite results, including MTD and maximum symptom (defined as the most severe of any recorded symptom for that food challenge), will be listed for each DBPCFC for all enrolled subjects, including screen failures. Indeterminate results will be indicated.

The peanut MTD at Screening and Exit DBPCFCs, last dose achieved, number of days at last dose (excluding any time at that dose level prior to an escalation or deescalation, and excluding any time after an Exit DBPCFC), and whether the subject was an escalation failure (per Tables 7.1 and 7.2) will also be listed. Imputed peanut MTD at the Exit DBPCFC will be flagged. Desensitization response status and response subcategories for missed Exit DBPCFC and desensitization response will also be listed, as described in Section 7.3.

Dose levels administered during DBPCFCs will be summarized by time point and food challenge, by treatment group and overall for the Randomized and ITT populations.

## 9.3.1 Maximum Tolerated Dose at Exit DBPCFC

The Exit DBPCFC uses a modified PRACTALL dosing regimen. PRACTALL doses are approximately on a logarithmic scale (3 mg, 10 mg, 30 mg, 100 mg, 300 mg). The highest dose level, 600 mg, was chosen in lieu of the 1000 mg dose level from the PRACTALL guidance to further insure safety. Each single PRACTALL dose step corresponds to a 3 to 3.33-fold (roughly 3.16-fold) increase in dose or a 0.477 to 0.523 (roughly 0.5) increase in the log10 scale. The 600 mg dose level is 2-fold increase in dose or approximately a 0.3 increase in the log10 scale above the 300 mg dose. Each increase of 2 PRACTALL dose steps (e.g. 30 to 300 mg or 10 to 100 mg) corresponds to a 10-fold increase in dose or an increase of 1 unit in the log10 scale. Subjects that cannot tolerate the lowest Exit DBPCFC dose will be set to 0.3 mg (a 1 unit decrease from the 3 mg dose, on the log10 scale) for purposes of analysis to allow for the logarithmic transformation. The MTD for the Exit DBPCFC will be imputed using the rules in Section 7.3 for all subjects with a missing Exit DBPCFC.

Estimates for the probability of tolerating each dose or higher will be based on the discrete hazards model with terms for treatment group effect and the MTD at the Screening DBPCFC (baseline) in the log10 scale. The extreme value hazard function will be used for the model. The probability estimates will be tabulated by treatment group and adjusted for the MTD at baseline. The adjusted probability estimates will be calculated at the median of the MTD at baseline. The adjusted probability estimates will also be plotted. An unadjusted probability estimate will also be calculated by removing the MTD at baseline term from the model. All subjects in the analysis population are considered eligible for the 1 mg dose. Subjects who did not receive the optional 1 mg dose at the Exit DBPCFC will be considered to have successfully passed that dose level and be eligible for the 3 mg dose level.

The treatment group effect will be assessed using the model with both terms to adjust for the MTD at baseline. The hazard ratio for the treatment group effect with its 95% confidence interval and the p-value will be based on the Wald statistic.

The maximum symptom severity at each dose level, and the cumulative maximum severity at each dose level, will be summarized by treatment group.

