3.3 Exit DBPCFC

All subjects who reach the targeted daily dose of 300 mg/day and maintain that dose for 2 weeks will undergo an exit DBPCFC. The exit DBPCFC will be performed in accordance with PRACTALL guidelines, but requiring progression in an unaltered sequence (Table 6-2), without repeating any dose.

Each subject will be unblinded after he/she completes the DBPCFC.

Subjects who do not reach the target dose by Week 34 are not eligible for the exit DBPCFC, and will be considered escalation failures. They will be unblinded no sooner than Week 24.

All placebo subjects are eligible for rollover into ARC002. Placebo subjects enrolled in ARC002 will undergo an escalation schedule identical to that for active subjects in the ARC001 protocol. All subjects on active treatment who pass the DBPCFC are eligible to proceed to ARC002. Subjects in the active treatment group who do not pass the DBPCFC at the 300 mg (443 mg cumulative) protein level will be considered endpoint failures and will not be eligible for rollover into the ARC002 protocol.

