## **3.2 Schedule of Study Assessments**

## 3.2.1 Screening Period

The screening visits (Visit 00) may occur over several days, and will include an initial DBPCFC. The DBPCFC will have both a peanut challenge and a placebo challenge, using up to 100 mg (143 mg cumulative) each of peanut protein and placebo, based on the PRACtical issues in ALLergology Joint United States/European Union Initiative (PRACTALL) dosing regimen, as shown in Table 3.1. At the investigator's discretion, a 1 mg dose may be added at the beginning of the escalation.

Challenge Doses					
	Peanut flour with				
Peanut Protein	50% protein content				
(mg)	(mg)				
3	6				
10	20				
30	60				
100	200				

Table 3.1. PRACTALL Screening DBPCFC Dosing Schedule

A DBPCFC is conducted either as two challenges during a single day visit (with at least 3 hours separating the two halves of the challenge) or over 2 days with the placebo challenge on one day and the peanut challenge on the other day. The food challenges are presented in random order and are performed under double-blind conditions.

Subjects who have dose-limiting symptoms at or before the 100 mg dose of peanut protein will be enrolled into the study. Those who successfully consume a dose of 100 mg of peanut protein during the Screening DBPCFC, without experiencing dose-limiting symptoms, will be considered screen failures and will not be randomized. Any subject who is assessed to have had dose-limiting symptoms to both parts of the Screening DBPCFC (i.e., to placebo [oat flour] as well as peanut flour) will be considered to be a screen failure and will not be randomized.

Subjects who meet eligibility criteria will return for a baseline visit, which may occur over multiple days. See Table 3.5 for the schedule of assessments.

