#### 4 SAMPLE SIZE CONSIDERATIONS

Sample size calculations are based on the primary efficacy analysis of the desensitization response rate. A true placebo response rate of 25% or less among subjects who undergo the Exit DBPCFC is assumed. Those individuals who fail to achieve the daily dose target or withdraw prematurely will be treated as non-responders. This study will enroll approximately 50 subjects randomly assigned in a 1:1 ratio of active to placebo.

If 3 subjects in each arm (about 12%) do not undergo the Exit DBPCFC, then the effective placebo response rate in the ITT analysis is assumed to be 22% or less. With a 2-tailed (alpha=0.05) test, there is at least 80% power to detect an effective CPNA response rate of 58.7 % or more, which corresponds to a CPNA response rate of 66.7% or more among those who undergo the Exit DBPCFC.

If 5 subjects in each arm (about 20%) do not undergo the Exit DBPCFC, then the effective placebo response rate in the ITT analysis is assumed to be 20% or less. With a 2-tailed (alpha=0.05) test, there is at least 80% power to detect an effective CPNA response rate of 56.6% or more, which corresponds to a CPNA response rate of 70.75% or more among those who undergo the Exit DBPCFC.

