#### 7.3 Maximum Tolerated Dose at DBPCFCs and Escalation Failures

The MTD for a DBPCFC is defined as the maximum single dose of peanut protein resulting in no more than mild symptoms and assessed by the investigator to have been tolerated (i.e., subject did not experience any dose-limiting symptoms). The MTD at the Screening DBPCFC will be used as the baseline amount of peanut protein tolerated. If a subject is administered non-standard doses at DBPCFC (i.e., other than the doses listed in Tables 3.1 or 3.4), the MTD will be considered the highest tolerated standard dose (i.e., 3 mg, 10 mg, 30 mg, 100 mg for either DBPCFC; 300 mg for Exit DBPCFC) which is tolerated.

An escalation failure is a subject who does not reach the target 300 mg/day dose by Week 34, or fails to complete at least a 2-week maintenance at that dose level.

Where necessary, desensitization response and MTD at the Exit DBPCFC will be imputed for subjects who do not have an Exit DBPCFC as shown in Table 7.1. As a general rule, subjects who do not undergo an Exit DBPCFC for any reason will be categorized as desensitization non-responders; and the imputed value for their MTD will be the maximum dose of peanut protein they tolerated in their Screening DBPCFC. The one exception to this rule is in the event of documentation that a subject introduced ad libitum peanut consumption into their diet and tolerated amounts of peanut exceeding a single peanut kernel (the targeted level of desensitization in the study). Although subjects are repeatedly and strenuously admonished, per protocol, to maintain a peanut-avoidant diet, there is always the potential for the admonishments to go unheeded, as well as for accidental exposure. In the unlikely event that a subject starts to consume peanut ad libitum before exiting the trial, whether or not this occurs as the result of a protocol violation, provision has been made for imputing their results (see Table 7.1). If, however, the amount of peanut consumed and tolerated by a subject claiming ad *libitum* peanut consumption cannot be ascertained from the eCRF or source documentation, then the subject will be classified as a non-responder who missed their Exit DBPCFC after having discontinued for reasons unrelated to treatment. If a subject added ad libitum peanut consumption to their diet and had additional reasons for missing the Exit DBPCFC, then the imputation rules for ad libitum

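### SAP 9.3.1 derives both the adjusted and the unadjusted probability of tolerating each exit dose from one hazard ratio across all dose steps, unchecked, so dose-specific treatment differences can be misstated

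*SAP*

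**What the plan says.** For the first key secondary endpoint, SAP 9.3.1 states: "Estimates for the probability of tolerating each dose or higher will be based on the discrete hazards model with terms for treatment group effect", together with the Screening MTD on the log10 scale. The link is fixed: "The extreme value hazard function will be used for the model". That is the complementary log-log form, which means proportional hazards over the dose steps. One treatment effect is reported: "The hazard ratio for the treatment group effect with its 95% confidence interval and the p-value will be based on the Wald statistic". The second set of probabilities comes from the same model: "An unadjusted probability estimate will also be calculated by removing the MTD at baseline term from the model". It still has a single hazard ratio and is not the observed data.

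Three other rules determine the data this model will see.
- Protocol 3.3: "All subjects who reach the targeted daily dose of 300 mg/day and maintain that dose for 2 weeks will undergo an exit DBPCFC".
- SAP 3.2.1: "Subjects who have dose-limiting symptoms at or before the 100 mg dose of peanut protein will be enrolled into the study". Subjects who tolerate 100 mg are screen failures, so the baseline MTD is at most 30 mg.
- SAP 7.3, for subjects without an exit challenge: "the imputed value for their MTD will be the maximum dose of peanut protein they tolerated in their Screening DBPCFC". Documented ad libitum peanut consumption is the exception and is scored 300 mg.

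SAP 9.3.2 plans unequal-slopes and normality checks for the ANCOVA. Section 9.3.1 lists no treatment-by-dose term and no check of proportionality.

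**The concern.** The CPNA arm is a mixture. Challenged CPNA subjects already take 300 mg a day, so they can be expected to fail late in the challenge. Unchallenged CPNA subjects are scored at their Screening MTD and so fail at or before the 100 mg step, as placebo subjects do. Such a mixture tends to give a strong treatment effect at the low steps and a weak one at the top. A single hazard ratio averages the two and moves apparent benefit from some doses to others.

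The affected outputs are those titled as the probability of tolerating each exit dose (Tables 14.2.10-14.2.13, Figures 14.2.23-14.2.26). Readers will use them to judge protection at small accidental exposures, which Protocol 1.1 gives as the goal of the programme. The 300 mg row may also disagree with the primary response rate, and the plan does not say which figure to use if it does.

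**Working it through.** **1. The plan's own figures.** SAP 4 assumes 25 subjects per arm. For placebo: "A true placebo response rate of 25% or less among subjects who undergo the Exit DBPCFC is assumed".
- With 3 per arm unchallenged: 0.25 × 22/25 = 22% against 0.667 × 22/25 = 58.7%.
- With 5 per arm unchallenged: 0.25 × 20/25 = 20% against 0.7075 × 20/25 = 56.6%.
- Exact power of the uncorrected Pearson chi-square test, enumerating two binomials with n = 25, is 80.0% and 80.2%. This agrees with the stated 80%.

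The documents give no rates at 30, 100 or 600 mg, so everything below 300 mg and at 600 mg is assumed.

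**2. Formulas.** Let S(k) be the proportion with MTD at or above dose k. On the complementary log-log scale the hazard at step k is −ln[S(k)/S(k−1)], and the step hazard ratio is CPNA over placebo. The planned model forces S_CPNA(k) = S_placebo(k)^HR, with the same HR at every k. I assume a separate intercept for each step, which the SAP does not spell out.

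**3. Illustration at the 12% planning case.** Assumed:
- Screening MTDs are spread evenly over below 3, 3, 10 and 30 mg. The 12% unchallenged CPNA subjects then lose 3 points at each step from 3 to 100 mg.
- Challenged CPNA subjects fail only at 300 mg or above: 0.88 × 0.667 = 58.7%.
- Half of those who pass 300 mg also pass 600 mg.
- Half of placebo failures improve on their Screening MTD, giving the placebo column below.

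Large-sample fit without the baseline term, HR = 0.39 (percent; differences in points):

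| Dose (mg) | True CPNA / placebo | True difference | Step HR | Model CPNA / placebo | Model difference | Error |
|---|---|---|---|---|---|---|
| 3 | 97.0 / 87.1 | 9.9 | 0.22 | 95.4 / 88.6 | 6.8 | −3 |
| 10 | 94.0 / 72.1 | 21.9 | 0.17 | 89.8 / 76.0 | 13.8 | −8 |
| 30 | 91.0 / 54.4 | 36.6 | 0.12 | 82.8 / 61.7 | 21.1 | −15 |
| 100 | 88.0 / 32.6 | 55.4 | 0.07 | 73.1 / 44.8 | 28.3 | −27 |
| 300 | 58.7 / 22.0 | 36.7 | 1.03 | 55.1 / 21.7 | 33.4 | −3 |
| 600 | 29.3 / 11.0 | 18.3 | 1.00 | 33.7 / 6.2 | 27.5 | +9 |

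Example at 100 mg: CPNA −ln(0.880/0.910) = 0.0335; placebo −ln(0.326/0.544) = 0.512; ratio 0.07. At 300 mg: 0.405/0.393 = 1.03. The model's 100 mg value is 0.448^0.39 = 0.731.

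**4. A milder case.** Take 20% unchallenged, 70.75% of challenged CPNA subjects passing 300 mg, and 30% of CPNA challenge failures below 300 mg. The errors are −8 points at 30 mg, −14 at 100 mg, −6 at 300 mg and +7 at 600 mg.

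**5. Range at the planning rates.** The grid had 486 scenarios. It varied the screening MTD profile, 12% or 20% unchallenged, where CPNA failures fall, how many placebo failures improve, and the share passing 600 mg in each arm. Errors of the unadjusted model in points:

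| Dose (mg) | Median | 10th to 90th percentile | Full range | Share understated |
|---|---|---|---|---|
| 30 | −8.6 | −22 to +2 | −39 to +11 | 85% |
| 100 | −15.6 | −31 to −2 | −48 to +12 | 93% |
| 300 | −4.8 | −18 to +7 | −26 to +13 | 68% |
| 600 | +6.5 | −1 to +15 | −6 to +21 | 12% |

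A narrower set of 72 scenarios gave 0 to −27 points at 30 mg, +6 to −32 at 100 mg, +4 to −10 at 300 mg and 0 to +10 at 600 mg.

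**6. The model-free alternative.** In simulation with 25 per arm, under the cases in steps 3 and 4, the observed cumulative proportions were within 0.3 points of the truth at every dose.

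**The case against.** The case for leaving the plan alone has real content.

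- **Model-free results are already planned.** SAP 9.3.2 gives frequencies for each exit MTD level, and Table 14.2.9 gives dose levels tolerated by arm. The primary analysis at 300 mg does not use this model. The addendum's Completer tables largely remove the imputed subjects. This limits the harm, but the tables and figures titled as tolerance probabilities remain model-based, and the unadjusted rows look like observed data when they are not.
- **The planned effect measure is the hazard ratio.** No between-arm difference in the probabilities is specified. That is true, but the probabilities are tabulated and plotted by arm, so readers will take the difference.
- **The plotted estimates are adjusted.** They are evaluated at the median baseline MTD, while the ranges above are for the unadjusted fit. Adding the baseline term does not remove the misfit: against the same true differences, the median errors over the 486 scenarios were −7.8 points at 30 mg and −14.8 at 100 mg.
- **The size is not known.** This stands. A reader might infer a definite understatement, such as 5 to 14 points at both doses. The documents give no MTD distribution below 300 mg, and only 9% of scenarios put both doses in that band.
- **Full treatment-by-step terms may not be estimable.** This also stands. With even screening MTDs and CPNA failures at 3 and 10 mg coming only from imputed subjects, the chance that at least one of those two cells is empty is 2(0.97^25) − 0.94^25 = 72% with 12% unchallenged. With 20% unchallenged it is 2(0.95^25) − 0.90^25 = 48%.

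**Conclusion.** The concern holds as a point about estimation. One hazard ratio, with no check, produces every tabulated and plotted tolerance probability, and the plan's own challenge and imputation rules make a constant ratio unlikely. At the planning rates the unadjusted model usually understates the treatment difference at 30 and 100 mg, from roughly none to about 30 points, with wider extremes under some assumptions. It tends to overstate the difference at 600 mg and need not match the primary response rate at 300 mg. These sizes rest on assumed screening MTDs, failure doses and 600 mg pass rates.

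Three stronger readings are not supported.
- A reader might say the rules contradict proportional hazards. They make it unlikely; late failure among challenged CPNA subjects is an expectation, not a rule.
- A reader might treat understatement as certain. The sign can reverse. With 5% placebo and 95% CPNA response among those challenged, and 4% against 20% unchallenged, the model overstates by 9 points at 30 mg and 3 at 100 mg.
- A reader might conclude that the key secondary test fails. With no treatment effect on the analysed MTD, the ratio is 1 at every step, so this misfit alone does not invalidate the Wald test or the testing hierarchy. The primary analysis is untouched.

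**What to change.** 1. In Tables 14.2.10-14.2.13 and their Completer repeats, replace the unadjusted model rows with the observed proportion whose MTD (imputed where SAP 7.3 says so) is at or above each dose, by arm, with Wilson 95% intervals. The 300 mg row then equals the primary response rate. If the primary analysis switches to exact intervals under SAP 9.1, use the same type in that row.
2. Plot these proportions beside the adjusted curves in Figures 14.2.23-14.2.26.
3. Add a check of the single hazard ratio, using treatment by dose step or treatment by log10 dose, and report it with the model.
4. Keep the single-hazard-ratio model for the overall test, the summary hazard ratio and the adjusted probabilities, labelled as assuming proportional hazards. Do not require full treatment-by-step terms in the adjusted model, because empty CPNA cells at low doses can make them inestimable with 25 per arm.
5. Settle the handling of undocumented ad libitum consumption. The text of SAP 7.3 classes such a subject as a non-responder who missed the exit challenge, which leads to the Screening MTD, while footnote 4 of Table 7.1 imputes nothing. The observed proportions need one denominator.

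The cost is SAP wording, minor programming and somewhat wider intervals at some doses.

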## 9.3.2 Change from Baseline in MTD at Exit DBPCFC

Summary statistics will be reported for Screening DBPCFC (baseline), Exit DBPCFC, and change in MTD for the DBPCFC in the  $log_{10}$  dose scale. Results in the  $log_{10}$  scale will be transformed back to the original scale to also report summary statistics in the original scale. Frequencies and percent of subjects will also be presented for each MTD level at the Screening and Exit DBPCFC. Similarly, frequencies and percent of subjects will be presented for all possible ratios (X-fold increase) of the MTD at the Exit DBPCFC relative to baseline.

Analyses of change from baseline MTD will be performed using change calculated on the log10 scale. An analysis of covariance (ANCOVA) model of change from baseline MTD at Exit DBPCFC ( $log_{10}$  mg) will be fit with terms for treatment group and the MTD at baseline ( $\log_{10}$  mg). The baseline adjusted least squares means with 95% confidence intervals by treatment group and for the treatment group difference will be tabulated. The p-value is based on the F-test for treatment group effect adjusted for the MTD at baseline (log10 mg). The ANCOVA model will also be assessed for unequal slopes by adding a term for the treatment group by baseline interaction and using an F-test to test for unequal slopes. If there is a signal of unequal slopes at the 0.10 significance level, then the least squares means with 95% confidence interval, and p-value for the F-test of the treatment group difference will be calculated and reported at baseline MTDs of 1 mg, 3 mg, 10 mg, and 30 mg. P-values and confidence intervals are based on the normality assumption. Residuals for ANCOVA will be assessed for non-normality using the Shapiro-Wilk test. If significant at the 0.05 level, then the Wilcoxon rank sum statistic will be used to test for a treatment group difference to examine the robustness of the ANCOVA F-test. Further exploration may be warranted if unequal slopes are noted.

Least squares mean statistics (point estimates and confidence intervals) from the ANCOVA analysis of change from baseline analysis in the log10 scale will be transformed back to the original scale to obtain geometric least squares mean statistics by treatment group of the ratio of the MTD at the Exit DBPCFC to baseline.

